6.6. Safety Analyses

All safety analyses will be performed based on the safety analysis set. Safety and tolerability will be assessed, where applicable, by incidence, severity, and change from baseline values for all relevant parameters including AEs, laboratory values, vital signs, ECG findings. Summaries will be separated for dinutuximab and 13-cis-RA only for extent of exposure and related treatment emergent adverse events (TEAEs, as defined in [Section 6.6.2](#)).

6.6.1. Extent of Exposure

The following measures of the extent of exposure will be summarized separately for dinutuximab and 13-cis-RA:

- Duration of exposure (days): calculated as following:
 - For dinutuximab: earlier of (last dose date + 24 days, data cutoff date) + 1 - first dose date

- For 13cis-RA: earlier of (last dose date + 21 days, data cutoff date) + 1 - first dose date
- Number of treatment cycles received: defined as the number of the last treatment cycles in which at least one dose of the study drug is administered.
- Total dose received per patient (mg/m² and mg): defined as the cumulative dose of the study drug during the treatment period of the study, with and without BSA adjustment.
- Actual dose intensity per cycle (mg/m²/cycle): defined as the total dose received by a patient divided by the number of treatment cycles received.
- Relative dose intensity per cycle (%): defined as the total dose received divided by protocol specified planned total dose for 5 cycles.
- Dose reduction
 - Number of dose reductions and reasons
 - Number of dose-reduced cycles
- Dose interruption
 - Number of dose reductions and reasons
 - Number of dose-interrupted cycles
- Dose delay and reason

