- To assess the safety and tolerability of ≤ 5 treatment cycles of dinutuximab beta in combination with 13-cis-retinoic acid (RA) as maintenance therapy in Chinese patients with high-risk neuroblastoma
- To characterize the pharmacokinetics (PK) of dinutuximab beta in Chinese patients

Exploratory:

• To explore the preliminary anti-tumor activity and event free survival rate (EFS), of ≤ 5 treatment cycles of dinutuximab beta in combination with 13-cis-RA as maintenance therapy in Chinese patients with high risk neuroblastoma, if applicable

Study Endpoints:

Primary:

- Adverse events (AEs) characterized by type, frequency, severity (as graded by the National Cancer Institute-Common Terminology Criteria for Adverse Events [NCI-CTCAE] version 5.0), timing, seriousness, and relationship to study drug(s); and other safety assessments
- PK parameters of dinutuximab beta, including but not limited to area under the concentration-time curve (AUC), maximum serum concentration (C_{max}), minimum serum concentration (C_{min}), time to C_{max} (t_{max}), and half-life (t_{1/2}) if data permits

Exploratory:

• EFS is defined as the time from initiating study drug(s) to disease progression, death from any cause, relapse, secondary malignancy as assessed by investigators, including EFS rate at 6 months as measured by Kaplan-Meier method

Study Design

This is an open-label, multi-center, single-arm, Phase 1 study evaluating the safety and pharmacokinetics of dinutuximab beta as maintenance therapy in Chinese patients with high-risk neuroblastoma.

After providing written informed consent, completing all screening assessments, and being confirmed as eligible for study participation, approximately 8 patients will be enrolled to receive dinutuximab beta plus 13-cis-RA therapy:

- Dinutuximab beta at 100 mg/m²/cycle will be given as continuous long-term infusion (LTI) for 10 days from Day 1 to Day 11 in every 35-day cycle.
- Patients will receive 13-cis-RA 160 mg/m²/day, divided into close to 2 equal doses and given orally twice a day for 14 days, starting on the next day after completion of dinutuximab beta infusion.
- Up to 5 cycles of administration will be applied for both dinutuximab beta and 13-cis-RA.

Study Assessments:

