- AEs will be characterized by type, frequency, severity (as graded by the NCI CTCAE version 5.0), timing, seriousness, and relationship to study drug will be recorded; other safety assessments to be performed including vital signs, physical examinations, ophthalmologic examination, performance status, laboratory safety tests, etc.
- Blood samples will be collected on Day 1, 3, 8, 11, 15 (optional), 22 (optional), and 29 in Cycle 1, and on Day 1 and 11 in Cycle 2, 3, and 4 to characterize the PK of dinutuximab beta.
- Tumor assessments or monitoring will be performed by the investigators at Screening Visit, end of treatment Cycle 3, and end of treatment visit. International Neuroblastoma Response Criteria (INRC) (Brodeur et al 1993) is recommended as a reference for response evaluation in patients evaluable for tumor assessment.

Duration of Patient Participation:

Patients will receive study drugs until the completion of the 5 treatment cycles (ie. 25 weeks), tumor relapse, progressive disease (PD), unacceptable toxicity, death, or other discontinuation criterion is met.

Study Population:

Patients aged \geq 12 months with high-risk neuroblastoma who have previously received induction chemotherapy and achieved at least a partial response followed by myeloablative therapy and stem cell transplantation

Key Eligibility Criteria:

- Patients aged ≥ 12 months
- Diagnosis of high-risk neuroblastoma according to the International Neuroblastoma Staging System (INSS) criteria, ie, INSS Stage 4 without *MYCN* amplification (MNA) and aged ≥ 18 months; or INSS Stage 2-4 with MNA
- Patients who have previously received induction chemotherapy and achieved a partial or complete response followed by myeloablative therapy and stem cell transplantation

Investigational Products, Dose, and Mode of Administration:

Dinutuximab beta

- Dinutuximab beta at 100 mg/m²/cycle will be given as continuous long-term infusion (LTI) for 10 days from Day 1 to Day 11 in every 35-day cycle.
- Up to 5 cycles of infusion will be administered.

13-cis-RA

- 13-cis-RA will be given orally at a dose of 160 mg/m²/day, divided into close to 2 equal doses twice a day for 14 days, started on the next day after completion of dinutuximab beta infusion.
- Up to 5 cycles of oral administration will be applied.

Reference Therapy, Dose, and Mode of Administration:

Not applicable

Statistical Methods:

Analysis Sets

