3. STUDY DESIGN

3.1. Summary of Study Design

This is an open-label, multi-center, single-arm, Phase 1 study evaluating the safety and pharmacokinetics of dinutuximab beta as maintenance therapy in Chinese patients with high-risk neuroblastoma.

Potential patients will be screened for eligibility before study enrollment (screening period ≤ 28 days). The study will recruit approximately 8 patients who will be hospitalized (with a full resuscitation equipment) on Day 1 of each cycle and will receive continuous infusion of dinutuximab beta administered at a dose of 10 mg/m²/day for 10 consecutive days in 35-day cycles (total dose 100 mg/m²/cycle). Patients must be administered in a unit with a full resuscitation equipment. Patients will be discharged from the hospital at the investigator's discretion. Patients will continue to receive 13-cis-RA 160 mg/m²/day, divided into close to 2 equal doses and given orally twice a day for 14 days after completion of dinutuximab beta infusion.

[figure not shown]
Patients may receive up to five 35-day cycles in the absence of relapse, disease progression or unacceptable toxicity.

Refer to Figure 1 for an overview of the study design and Appendix 1 for details on study assessments and procedures that will be carried out during the study.

The maximum duration of participation (Screening Visit to Safety Follow-up Visit) for individual patients will be approximately 35 weeks. Each patient will participate in the screening period (\leq 28 days), study intervention infusion period (\leq 25 weeks), and a post-infusion period (\leq 6 weeks). Additional clinical follow-up might be needed depending on findings during the study.

Figure 1: Study Schema

- Dinutuximab beta intravenous infusion (continuous infusion from Day 1 to Day 11 of each cycle)
- 13-cis-retinoic acid orally twice a day for 14 days, starting from the next day after completion of dinutuximab beta (Day 12 to Day 25) in each cycle

Abbreviations: EOT, end of treatment; PK, pharmacokinetic(s).

All patients will be closely monitored for AEs throughout the study and for 40 days after the last dose of study drug. AEs will be graded according to the NCI-CTCAE version 5.0. Refer to Section 9 for additional and specific information regarding AE monitoring and reporting.

PK analysis will be performed for dinutuximab beta.

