5.2.1. Dinutuximab Beta

Dosage

Total dose: 100 mg/m²/cycle

Patients may receive up to five 35-day cycles in the absence of disease progression or unacceptable toxicity.

Dinutuximab beta is administered at a dose of 10 mg/m²/day as a 24-hour continuous infusion for 10 days (total dose 100 mg/m²/cycle) for five 35-day cycles.

Preparation of Infusion

The solution for infusion must be prepared under aseptic conditions. The solution must not be exposed to direct sunlight or heat.

The patient-specific daily dose of dinutuximab beta is calculated based on BSA. Dinutuximab beta should be diluted aseptically to the patient-specific concentration/dose with sodium chloride 9 mg/mL (0.9%) solution for infusion, containing 1% human albumin (eg, 5 mL of 20% human albumin per 100 mL of 0.9% sodium chloride solution).

For continuous infusions, the solution for infusion can be prepared freshly on a daily basis, or sufficient for up to 5 days of continuous infusion. The daily dose is 10 mg/m². The amount of solution to be infused per day (within a treatment course of 10 consecutive days) should be 48 mL; with 240 mL for a 5-day dose. It is recommended to prepare 50 mL solution in a 50 mL syringe, or 250 mL in an infusion bag suitable for the employed infusion pump, ie, an overfill of 2 mL (syringe) or 10 mL (infusion bag) to allow for dead volumes of the infusion systems.

Administration of The Infusion

The solution for infusion should be administered via a peripheral or central intravenous line. Other intravenously co-administered agents should be delivered via a separate infusion line. The container should be inspected visually for particulates before administration. It is recommended that a 0.22 micrometer in-line filter is used during infusion.

For continuous infusions, any medical device suitable for infusion at a rate of 2 mL per hour can be applied, eg, syringe infusion pumps/infusors, electronic ambulatory infusion pumps. Note that elastomeric pumps are not considered suitable in combination with in-line filters.

The investigator may need to reduce or delay doses or stop treatment if certain side effects occur. It allows the investigator to decrease at 50% of the previous dose or interrupt the infusion. In this instance, the total amount does not need to equal 240 hours of infusion per cycle ideally (total dose of 100 mg/m²/cycle). The investigator must record the reasonable reason for providing any alternative dose during treatment.

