5.4. Dose Delay or Modification

Dose modification

This protocol allows some alteration from the currently outlined infusion schedule of dinutuximab beta, but the maximum cumulative exposure will not exceed 100 mg/m²/cycle.

Based on the Investigator's evaluation of the severity of adverse drug reactions to dinutuximab beta, patients may undergo a dose reduction of 50% or a temporary interruption of the infusion. As a consequence, either the infusion period is prolonged or, if tolerated by the patient, the infusion rate may be increased up to 3 mL/h (continuous infusion), in order to administer the total dose.

Regarding the dose modification of 13-cis-RA, please refer to local label of 13-cis-retinoic acid.

Table 3: Recommended Dinutuximab Beta Dose Modification

Adverse reaction	Severity	Treatment modification
Any	Grade 1 or 2	Decrease infusion rate to 50%. After resolution, resume infusion at original rate.

Hypersensitivity reaction	eg, Hypotension	Interrupt infusion and administer supportive measures. After resolution, resume infusion at original rate.
Dilated pupils with sluggish light reflex ± photophobia		Interrupt infusion. After resolution, resume infusion at 50% rate.
Any	≥ Grade 3	Interrupt infusion and administer supportive measures. Resume infusion at 50% rate if adverse drug reaction (ADR) resolves or improves to Grade 1 or 2 within 3 days of onset. If 50% dose reduction is tolerated for ≥ 1 day, consider advancing infusion to full rate as tolerated. If toxicity (≥ Grade 3) recurs at 50% dose reduction, treatment should be discontinued. If toxicity (≥ Grade 3) recurs while at 100% infusion rate, stop infusion and reduce dose to 50% if toxicity resolves or improves to ≤ Grade 2 within 3 days of onset. Do not increase dose to 100% again.
Capillary leak syndrome		Interrupt infusion and administer supportive measures. Resume at 50% rate if ADR resolves or improves to Grade 1 or 2.
Capillary leak syndrome requiring ventilator support; allergic reaction (anaphylaxis), skin toxicity, severe neuropathic pain, any other Grade 4 toxicity (which does not recover to Grade 1 or 2 or baseline within 5 weeks)	Grade 4	Discontinue infusion. Contact sponsor to confirm if patient may continue infusion at the start of the subsequent cycle.

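### The SAP's duration-of-exposure formulas omit date of death, so up to 24 days (dinutuximab beta) or 21 days (13-cis-RA) after death can be counted as exposure

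*SAP*

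**What the plan says.** SAP 6.6.1 (Extent of Exposure) defines duration of exposure separately for the two drugs:

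- Dinutuximab beta: "earlier of (last dose date + 24 days, data cutoff date) + 1 - first dose date".
- 13-cis-RA: "earlier of (last dose date + 21 days, data cutoff date) + 1 - first dose date".

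Each formula adds a fixed tail to the last dose date and truncates only at the data cutoff. Protocol 10.2.1 lists duration of exposure among the summaries but gives no formula. SAP Appendix 2 does limit imputed end dates of medications and adverse events to the last known alive date or end of study. That rule covers imputed dates of those two kinds only, not exposure.

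The planned schedule behind the constants is in the protocol. Dinutuximab beta is a "continuous long-term infusion (LTI) for 10 days from Day 1 to Day 11 in every 35-day cycle" (Synopsis). 13-cis-RA is given "starting from the next day after completion of dinutuximab beta (Day 12 to Day 25) in each cycle" (Section 3.1, Figure 1). Treatment runs "until the completion of the 5 treatment cycles (ie. 25 weeks") (Synopsis), unless a stopping reason comes first.

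**The concern.** The tail credits a patient with the rest of the cycle after the last dose. That is reasonable for someone who is alive and under observation, but it cannot apply to someone who has died. As written, a programmer following the SAP would output exposure that runs past the death date.

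Safety is a primary endpoint, and Protocol 10.2 uses extent of exposure in describing the safety profile. With about 8 patients and with minimum and maximum reported (SAP 6.3.2), one early death could set the reported minimum, and the value shown would be impossible. A reader comparing the exposure and death listings would see the contradiction.

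**Working it through.** **Inputs.** Study days count from the first dinutuximab beta dose. Cycle length is 35 days. The planned infusion ends on Day 11, and planned 13-cis-RA runs from Day 12 to Day 25 (Protocol Synopsis and 3.1). Tails are 24 and 21 days (SAP 6.6.1). Let F be the first dose date, L the last dose date, D the date of death and C the data cutoff. I take L for dinutuximab beta as the day the infusion ends, and C as later than the tail.

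**Step 1: on-schedule values.** SAP duration = L + tail + 1 − F.

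- Dinutuximab beta, one cycle: 11 + 24 + 1 − 1 = 35. Five cycles: L = 140 + 11 = 151, so 151 + 24 + 1 − 1 = 175.
- 13-cis-RA, one cycle: 25 + 21 + 1 − 12 = 35. Five cycles: L = 140 + 25 = 165, so 165 + 21 + 1 − 12 = 175.

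The planned figure is 5 × 35 = 175 days = 25 weeks. Both constants reproduce it, so they are right for a patient treated on schedule.

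**Step 2: death inside the tail.** Days counted after death = tail − (D − L), while this is positive.

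| Case | SAP | With death cap | Counted after death |
|---|---|---|---|
| Dinutuximab beta, L = Day 11, D = Day 15 | 35 | 15 | 20 |
| Dinutuximab beta, L = D = Cycle 3 Day 11 (Day 81) | 105 | 81 | 24 |
| Dinutuximab beta, L = Day 81, D = Day 88 | 105 | 88 | 17 |
| 13-cis-RA, L = D = Cycle 5 Day 25 (Day 165) | 175 | 154 | 21 |

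The error falls to zero once death is 24 days (dinutuximab beta) or 21 days (13-cis-RA) after the last dose.

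**Step 3: effect on the summary.** With 8 patients, one such death shifts the mean dinutuximab beta duration by at most 24/8 = 3.0 days, and the 13-cis-RA mean by at most 21/8 = 2.6 days. The Day 15 example shifts it by 20/8 = 2.5 days.

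**Step 4: meaning of last dose date.** The SAP does not define it for a continuous infusion, and Protocol 5.2.1 allows solution to be prepared for up to 5 days at a time. For an on-schedule single cycle:

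- End of infusion, Day 11: 35 days.
- Day 10: 10 + 24 + 1 − 1 = 34 days.
- Start of a second 5-day bag, Day 6: 6 + 24 + 1 − 1 = 30 days.

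Only the first reading matches the planned 35 days.

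**Step 5: prolonged infusion (note only).** Since 24 = 35 − 11, the tail assumes a Day 11 finish in the last treated cycle. Protocol 5.2.1 gives the daily volume: "The amount of solution to be infused per day (within a treatment course of 10 consecutive days) should be 48 mL". Ten days is 480 mL at 2 mL/h. Run wholly at 1 mL/h to completion, that takes 480 h = 20 days and ends on Day 21. One cycle then reads 21 + 24 + 1 − 1 = 45 days. If it happens in Cycle 5, L = 161 and the value is 185 days.

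**The case against.** The strongest case against acting is that little depends on this number. Under SAP 6.6.1, dose intensity divides by cycles received and relative dose intensity by the planned five-cycle dose. The treatment-emergent window in SAP 6.6.2 runs 40 days from the last dose. None of these uses duration of exposure. Deaths are summarized separately in SAP 6.6.2, and the error needs a death soon after dosing in a population required to have a life expectancy of at least 12 weeks (Protocol 4.1). All of that stands, and it sets the size of the point. It does not supply the missing cap.

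A reader might go further and infer that any slower infusion is reported as longer exposure, so that poor tolerability looks like more treatment. Protocol 5.4 does say "As a consequence, either the infusion period is prolonged", and Table 3 lists for Grade 1 or 2 reactions "Decrease infusion rate to 50%. After resolution, resume infusion at original rate". The documents do not support that reading, for four reasons:

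- The excess arises only if the infusion of the last treated cycle ends after Day 11. Prolongation in an earlier cycle adds nothing if later cycles stay on schedule (still 175 days).
- Section 5.4 also permits a rate of up to 3 mL/h. Five days at half rate deliver 120 mL; the other 360 mL at 3 mL/h take 120 h, and the infusion still ends on Day 11. Section 5.2.1 does not insist on the full 240 hours.
- A tail counted from the actual last dose is a defensible convention. Someone infused until Day 21 did receive drug for longer, and Protocol 1.2.2 puts the half-life at around 190 hours.
- Tolerability is shown by other items in the same section: reductions, interruptions, delays and dose intensity.

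**Conclusion.** The defect is real but minor. As written, SAP 6.6.1 can count up to 24 days (dinutuximab beta) or 21 days (13-cis-RA) after death, and nothing elsewhere in the documents prevents it. The documents give no death rate, so how often this would occur cannot be stated. It needs a death within the tail and a data cutoff after the death.

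The conclusion rests on reading last dose date as the calendar end of the infusion, which the SAP should state. The constants themselves are sound. The longer values after a prolonged final infusion (45 or 185 days at the extreme) follow from a legitimate convention and should be borne in mind when reading the table. They are not an error to be corrected.

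**What to change.** In SAP 6.6.1, define the exposure end date as the earliest of three dates: L + 24 days (dinutuximab beta) or L + 21 days (13-cis-RA), date of death if any, and data cutoff. Duration is that end date + 1 − F. Add one sentence stating that L for dinutuximab beta is the calendar date on which the infusion ends. Where a death date is partial, refer to the existing rule for deaths in SAP Appendix 2.

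Death cannot precede the last dose, so the cap never removes a dosing day. On-schedule results remain 35 and 175 days.

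Do not replace the tail with Day 1 of the last cycle + 34 days (or, for 13-cis-RA, its first dose of that cycle + 34 days). That would raise a patient stopped on Cycle 1 Day 1 from 25 to 35 days, and one stopped on Day 5 from 29 to 35. It would also leave 13-cis-RA unchanged after a half-rate Cycle 5 infusion. With 13-cis-RA on Days 162 to 175, the current rule gives 175 + 21 + 1 − 12 = 185 and the replacement gives 162 + 34 + 1 − 12 = 185.

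The cost is two edited lines and one definition. Death dates are already needed for event-free survival and the death summary, so no new data are required.

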10.2. Safety Analyses

Safety is the primary endpoint and will be assessed by AEs as characterized by type, frequency, severity (as graded by the NCI-CTCAE version 5.0), time, seriousness, and relationship to study drug(s), vital signs and laboratory abnormalities. Extent of exposures, Physical examinations, and ECG findings will also be used in determining the safety profile. TEAEs will be reported as the number (percentage) of patients with TEAEs by Medical Dictionary for Regulatory Activities (MedDRA) system organ class and preferred term. Descriptive summary statistics (eg, n, mean, standard deviation, median, minimum, and maximum for continuous variables; n [%] for categorical variables) and changes from baseline will be determined for laboratory parameters and vital signs.

Safety data will be summarized using the SAS.

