10.2.1. Extent of Exposure

Extent of exposure to each study drug will be summarized descriptively as the number of cycles received (number and percentage of patients), duration of exposure (days), cumulative total dose received per patient (mg), dose intensity, and relative dose intensity.

The number (percentage) of patients requiring treatment interruption, dose delay, and drug discontinuation because of AEs will be summarized. Frequency of the above dose adjustments and discontinuation will be summarized by category. Reasons for dose modifications will be summarized as well.

Patient data listings will be provided for all dosing records and for calculated summary statistics.

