2. STUDY OVERVIEW

This is an open-label, multi-center, single-arm, Phase 1 study evaluating the safety and pharmacokinetics of dinutuximab beta as maintenance therapy in Chinese patients with high-risk neuroblastoma.

[figure not shown]
Potential patients will be screened for eligibility before study enrollment (screening period ≤ 28 days). The study will recruit approximately 8 patients who will be hospitalized (with a full resuscitation equipment) on Day 1 of each cycle and will receive continuous infusion of dinutuximab beta administered at a dose of $10 \text{ mg/m}^2/\text{day}$ for 10 consecutive days in 35-day cycles (total dose $100 \text{ mg/m}^2/\text{cycle}$). Patients must be administered in a unit with a full resuscitation equipment. Patients will be discharged from the hospital at the investigator's discretion. Patients will continue to receive 13-cis-RA $160 \text{ mg/m}^2/\text{day}$, divided approximately into 2 equal doses and given orally twice a day for 14 days after completion of dinutuximab beta infusion.

Patients may receive up to five 35-day cycles in the absence of relapse, disease progression or unacceptable toxicity.

Refer to [Figure 1](#) for an overview of the study design and Appendix 1 for details on study assessments and procedures that will be carried out during the study.

The maximum duration of participation (Screening Visit to Safety Follow-up Visit) for individual patients will be approximately 35 weeks. Each patient will participate in the screening period (≤ 28 days), study intervention infusion period (≤ 25 weeks), and a post-infusion period (≤ 6 weeks). Additional clinical follow-up might be needed depending on findings during the study.

Figure 1: Study Schema

Abbreviations: EOT, end of treatment; PK, pharmacokinetic(s).

All patients will be closely monitored for AEs throughout the study and for 40 days after the last dose of study drug.

PK analysis will be performed for dinutuximab beta.

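### SAP 6.6.1 calls a share of the five-cycle plan 'relative dose intensity per cycle', so full-dose patients who stop early score 20 to 80%; its interruption count line is also miscopied

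*SAP*

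**What the plan says.** Protocol Section 10.2.1 lists the exposure measures for each study drug, among them "cumulative total dose received per patient (mg), dose intensity, and relative dose intensity". It gives no formula for the last two, so the SAP supplies the definitions.

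SAP Section 6.6.1 defines two consecutive measures, both labelled per cycle:

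- Actual dose intensity is "defined as the total dose received by a patient divided by the number of treatment cycles received".
- The relative measure is worded "Relative dose intensity per cycle (%): defined as the total dose received divided by protocol specified planned total dose for 5 cycles".

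SAP Section 2 makes five cycles an upper limit: "Patients may receive up to five 35-day cycles in the absence of relapse, disease progression or unacceptable toxicity". Protocol Section 7.6.1 also lets one drug continue when the other is stopped permanently before Cycle 5, and the SAP summarizes exposure separately by drug.

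Under both the dose reduction and the dose interruption headings, the first line in SAP Section 6.6.1 is "Number of dose reductions and reasons". The second line under interruption is "Number of dose-interrupted cycles". After naming treatment interruption, dose delay and discontinuation, Protocol Section 10.2.1 says: "Frequency of the above dose adjustments and discontinuation will be summarized by category. Reasons for dose modifications will be summarized as well". SAP Section 8 declares one departure from the protocol, dropping the summary of important deviations, and says nothing about interruptions.

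**The concern.** A percentage labelled relative dose intensity per cycle will be read as how much of the planned dose patients received in the cycles they had. With a fixed five-cycle denominator it answers another question: how much of the full planned course was delivered. A patient who took every scheduled dose and stopped early would look under-dosed within cycles, and the row cannot separate that patient from one who stayed on treatment at reduced dose.

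Safety and tolerability is a primary objective, and Protocol Section 10.2 says: "Extent of exposures, Physical examinations, and ECG findings will also be used in determining the safety profile". With about 8 patients, one early stop moves the mean visibly.

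The interruption line matters because interrupting the infusion is the first listed action in 4 of the 6 rows of Protocol Table 3: hypersensitivity, dilated pupils, any reaction of Grade 3 or higher, and capillary leak syndrome. That counts table rows, not how often interruptions will occur, and the table covers dinutuximab beta only.

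**Working it through.** **Inputs**

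- Dinutuximab beta (Protocol Section 5.2.1): 10 mg/m²/day × 10 days = 100 mg/m² per cycle, which reproduces the protocol's own figure. Five cycles: 5 × 100 = 500 mg/m².
- 13-cis-RA (Protocol Section 5.2.2): 160 mg/m²/day × 14 days = 2,240 mg/m² per cycle. Five cycles: 5 × 2,240 = 11,200 mg/m².

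The documents state no value for relative dose intensity.

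**Algebra.** Let T be total dose received, k cycles received and D planned dose per cycle. Actual intensity is T/k, and actual over planned intensity is T/(kD). The SAP percentage is T/(5D) = [T/(kD)] × (k/5). The factor k/5 carries the early stopping.

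**Full dose, stopping after k complete cycles**

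| k | Dinutuximab beta, mg/m² | 13-cis-RA, mg/m² | SAP ratio, either drug | Actual / planned intensity |
|---|---|---|---|---|
| 1 | 100/500 | 2,240/11,200 | 20% | 100% |
| 2 | 200/500 | 4,480/11,200 | 40% | 100% |
| 3 | 300/500 | 6,720/11,200 | 60% | 100% |
| 4 | 400/500 | 8,960/11,200 | 80% | 100% |
| 5 | 500/500 | 11,200/11,200 | 100% | 100% |

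**Different histories, one score.** Half dose for 4 cycles gives (50 × 4)/500 = 40%, and full dose for 2 cycles gives 200/500 = 40%. Divided by the planned dose for the cycles received, these become 200/400 = 50% and 200/200 = 100%.

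**Can the order reverse?** Half the cumulative dose in all five cycles gives 250/500 = 50%. A full-dose patient falls below that only by stopping after 1 or 2 cycles. Stopping at the first scheduled on-treatment tumor assessment, the end of Cycle 3, gives 60%. Two patients with the same number of cycles never reverse (20k% against 10k%). Half the cumulative dose is a limiting case, because Protocol Section 5.4 allows the infusion to be prolonged or sped up so that the total dose is given.

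**Effect on the summary.** The documents give no stopping rate, so the counts here are assumptions. If m of 8 full-dose patients stop after k cycles, the mean is [m × 20k + (8 − m) × 100]/8.

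| m | Mean, k = 3 | Median, k = 3 | Mean, k = 2 | Median, k = 2 |
|---|---|---|---|---|
| 1 | 95% | 100% | 92.5% | 100% |
| 2 | 90% | 100% | 85% | 100% |
| 3 | 85% | 100% | 77.5% | 100% |
| 4 | 80% | 80% | 70% | 70% |

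Actual over planned intensity is 100% in every cell.

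**Interruption line.** The count line is word for word the same under both headings, while the line after it differs correctly (reduced cycles, then interrupted cycles). A copying slip is an inference, but a strong one. As written, Section 6.6.1 keeps the number of interrupted cycles and loses the number of interruptions and their reasons.

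**The case against.** The strongest reply is that the fault lies in the label only. The SAP states its denominator in the same sentence as the name, the protocol gives no competing formula, and Protocol Section 5.2.1 describes the regimen as five cycles, so the share of the five-cycle dose is a legitimate quantity. That stands, and it is why the present ratio should be kept under another name. It does not make the current label true.

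The proposed ratio also adds little information. It is the actual-intensity row divided by a constant, and for dinutuximab beta the two show the same number (75 mg/m²/cycle is 75%). That is correct, but a relative intensity is by nature the actual intensity over the planned one, so the overlap is expected.

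Nor does the proposed ratio separate stopping from reduction completely. A cycle counts as received once any dose is given, so a patient at full daily dose who stops after Day 1 of Cycle 2 has 100 + 10 = 110 mg/m² over two counted cycles, or 110/200 = 55%. This residual limit stands. The figures in the first table apply to stops at the end of a cycle.

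Finally, the harm is small. Adjacent rows give cycles received, total dose and actual intensity, SAP Section 6.4.1 gives discontinuation reasons, and Protocol Section 10.2.1 promises listings of all dosing records. For interruptions, the heading makes the intent plain, and SAP Section 6.6.2 still reports adverse events leading to interruption. All of this limits the consequence without correcting either line.

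**Conclusion.** Both faults are real. Followed as written, the SAP produces a percentage that does not measure what its name says: 20, 40, 60 or 80% for a full-dose patient who stops after 1, 2, 3 or 4 complete cycles, for either drug, against 100% of planned intensity. These figures follow from the definitions and planned doses alone. The group means and medians rest on assumed stopping counts, and the median stays at 100% in those scenarios until half the patients stop.

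The interruption line leaves a protocol-specified summary out of the SAP without declaring it, most likely by a copying slip.

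The consequence is confined to descriptive exposure rows. No test, sample size or event-free survival estimate changes, and a careful reader could reconstruct much of the picture from neighbouring rows. Both lines should still be corrected, because exposure supports the safety assessment and the correction costs almost nothing.

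**What to change.** In SAP Section 6.6.1:

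1. Define relative dose intensity (%) as total dose received divided by the protocol-planned dose for the cycles received: cycles received × 100 mg/m² for dinutuximab beta, and cycles received × 2,240 mg/m² for 13-cis-RA.
2. Keep the present ratio beside it, renamed *percentage of planned 5-cycle dose received*. Both are needed: a patient who stops for toxicity after one full-dose cycle scores 100% on the first and 20% on the second, so the second keeps early stopping visible.
3. Under dose interruption, replace the first line with *Number of dose interruptions and reasons*.

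A table footnote saying that a partly given cycle counts as received would cover the mid-cycle case.

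The cost is two lines of SAP wording and one extra table row, plus the footnote if wanted. It needs no new data and no protocol change.
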